#### 4.1. Strata Misallocations

Participants who are randomized to the wrong stratum, in error, will have the incorrect stratum assignment remain in IMPALA but the clinical database will include the correct stratum. The latter will subsequently be used for all relevant analyses.

## 5. GENERAL METHODOLOGY AND CONVENTIONS

### 5.1. Hypotheses and Decision Rules

Statistical inference will be based on the primary endpoint: change from baseline in HbA1c at Week 16.

The null hypothesis is that there is no difference between PF-06882961 and placebo on the primary endpoint. The alternative hypothesis is that PF-06882961 is superior (i.e. greater reduction) to placebo on the primary endpoint.

The Type I error rate ( $\alpha$ -level) used for the statistical inference will be 5% (1-sided).

Each dose of PF-06882961 will be tested separately compared to placebo.

No adjustment for multiple comparisons will be made.

Similar hypotheses will be applied to the secondary endpoints (change from baseline in fasting plasma glucose/body weight at Week 16 & response as defined by an HbA1c <7% at Week 16), where the type I error rate will also be 5% (1-sided). Note the alternative

[REDACTED]

hypothesis for the response endpoint is that PF-06882961 is superior to placebo as shown by an odds ratio  $> 1$ . As above, each dose of PF-06882961 will be tested separately compared to placebo with no adjustment for multiple comparisons.

## 5.2. General Methods

The efficacy analyses will be based on the appropriate population for analysis (see Section 4).

### 5.2.1. Summary Analyses for Continuous Data

Continuous variables will be presented using summary statistics: number of observations, arithmetic mean, standard deviation, median, minimum and maximum values.

### 5.2.2. Summary Analyses for Categorical Data

Categorical variables will be presented using summary statistics: number of observations, counts and percentages.

### 5.2.3. Mixed Model Repeated Measures (MMRM)

The MMRM model will include treatment, time, strata (defined as metformin vs. diet and exercise alone CCI [REDACTED] and treatment-by-time interaction as fixed effects, baseline as a covariate and the baseline-by-time interaction with time fitted as a repeated effect and participant as a random effect.

An unstructured covariance matrix will be used to estimate the variances and covariance within participant across time points. If convergence is not obtained or model fit is not adequate, then other covariance structures will be investigated as necessary. The Kenward-Roger approximation will be used for estimating degrees of freedom for the model parameters.

*Missing values* (e.g. due to censoring) will be implicitly imputed as part of the MMRM model fitting.

The Least Squares Means (LSMeans) together with 90% confidence intervals, standard errors and 2-sided p-values will be obtained for each treatment at each time point.

Differences in LSMeans between each dose of PF-06882961 relative to placebo at each time point, together with 90% confidence intervals, standard errors and 2-sided p-values, will also be obtained.

Example SAS code is provided in Appendix 4.

### Statistical Model Diagnostics

[REDACTED]

The presence of outliers will be investigated for this model. An outlier will be defined as any response data value with a studentized (conditional) residual greater than 3, or less than -3. A listing will be presented of any participants meeting these criteria and will be included with standard SAS outputs. The assumptions of normality will be verified graphically using residual plots. For each fitted model, a set of conditional studentized residual plots will be produced, including residual plot, histogram of normality, QQ plot and summary of fit statistics. The residual plots will not be included in the clinical study report.

If there are outliers or major deviations from normality, then the effect of these on the conclusions may be investigated through alternative transformations and/or analyses excluding outliers. Justification for any alternative to the planned analysis will be given in the report of the study.

#### 5.2.4. Logistic Regression

*The logistic regression model will include a term for treatment, strata (metformin vs. diet and exercise alone), and baseline will be included as a covariate. The model will be fitted to the Week 16 timepoint only.*

Missing values (e.g. due to censoring) will be imputed for missing data using a multiple imputation method as described in Section 5.3.

The odds ratio for each dose of PF-06882961 relative to placebo and corresponding 90% confidence interval will be obtained.

Example SAS code is provided in Appendix 4.

#### 5.2.5. Emax Model (no baseline interaction)

The 4-parameter dose-response Emax model will be used to characterize change from baseline (CFB) dose-response relationships with dose included as a continuous variable.

The model structure will take the form:

$$CFB = E_0 + \frac{E_{max} \times dose^{Hill}}{ED_{50}^{Hill} + dose^{Hill}}$$

$E_0$  is the placebo effect,  $dose$  is the target randomized dose,  $E_{max}$  is the maximum effect,  $ED_{50}$  is the dose producing 50% of the maximum effect and  $Hill$  is the slope parameter.

The model will be applied to the LSMeans results from the primary MMRM model (Section 6.1.1.1) utilizing a Bayesian methodology approach with weakly informative priors as described in Appendix 3.

Estimates of the model parameters of  $E_0$ ,  $E_{max}$ ,  $ED_{50}$  and  $Hill$  and their 95% credible intervals will be produced.

The posterior medians and 90% credible intervals (5th and 95th percentiles of the relevant posterior distribution) will be reported for each target randomized dose (including Placebo) and their differences relative to placebo. Both will be reported in tables and plotted in separate figures.

If convergence cannot be obtained or visual inspection of the data does not support a dose-response  $E_{max}$  relationship the following options will be considered in order: (1) assume the hill parameter is 1 and remove from the model (giving a 3-parameter dose-response  $E_{max}$  model); (2) utilize alternative priors to those provided in the appendix; (3) otherwise an  $E_{max}$  model (no baseline interaction) will not be reported and alternative model structures may be investigated and the subsequent analyses may be included in the CSR with rationale for the eventual model selected.

#### **5.2.6. $E_{max}$ Model (baseline interaction)**

An additional 4-parameter dose-response  $E_{max}$  model will be used to characterize change from baseline (CFB) dose-response relationships, assuming an interaction between baseline HbA1c and dose.

The model structure will be the same as Section 5.2.5.

[figure not shown]
The model will be applied to the LSMean results from individual MMRM models that have been applied to each treatment separately. The MMRM models will include time and strata as fixed effects, baseline as a covariate and the baseline-by-time interaction with time fitted as a repeated effect and participant as a random effect.

An unstructured covariance matrix will be used to estimate the variances and covariance within participant across time points for each separate MMRM. If convergence is not obtained or model fit is not adequate, then other covariance structures will be investigated as necessary. The Kenward-Roger approximation will be used for estimating degrees of freedom for the model parameters.

The LSmean results from the separate MMRM models will be calculated for the overall baseline HbA1c (i.e. across all participants in the Estimand Set 1A) and then fitted with the  $E_{max}$  model above utilizing a Bayesian methodology approach with weakly informative priors as described in Appendix 3.

Estimates of the model parameters of  $E_0$ ,  $E_{max}$ ,  $ED_{50}$  and  $Hill$  and their 95% credible intervals will be produced.

The posterior medians and 90% credible intervals (5th and 95th percentiles of the relevant posterior distribution) will be reported for each target randomized dose (including Placebo)

and their differences relative to placebo. Both will be reported in tables and plotted in separate figures.

If convergence cannot be obtained or visual inspection of the data does not support a dose-response Emax relationship the following options will be considered in order: (1) assume the hill parameter is 1 and remove from the model (giving a 3-parameter dose-response Emax model); (2) utilize alternative priors to those provided in the appendix; (3) otherwise an Emax model (with a baseline interaction) will not be reported.

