#### 6.1.1.2. Sensitivity/Supplementary Analyses

For all of the following analyses, standard SAS output will be provided to support the statistical summaries produced but will not be included in the CSR.

The following supplementary analyses to the primary endpoint will be carried out:

- To assume a dose-response relationship with HbA1c (without a baseline interaction) an Emax model will be applied to the LSmeans at Week 16 from the main MMRM analysis as described in Section 5.2.5.
- To assume a dose-response relationship with HbA1c, including an interaction between baseline HbA1c and dose, an Emax model will be applied to the LSMeans at Week 16 from separate MMRM models at the overall baseline HbA1c as described in Section 5.2.6.

CCI

CCI

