### Emax model with baseline interaction (Section 5.2.6)

A dataset of the same format to above should be produced by programming for use in R by the reporting statistician and QC statistician. Note, column headers should be labelled as specified (including capitalization), as R is case sensitive.

The residual standard deviations at Week 16 from the unstructured covariance matrices from each of the associated MMRM models will also be provided to the statisticians.

The same process for priors, model fitting, checking of model convergence and QC as above will be implemented for this model along with similar R code as to above. The only major difference in R code is the requirement to take the average of the residual standard deviations from the separate MMRM outputs which will be used as the global standard deviation in model fitting:

```
mmrmDoseRes <- read.csv(Dose_LSmeans.csv",header=T,stringsAsFactors=F)  

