# Merge datasets:  
mmrmDoseRes <- merge(mmrmDoseRes,mmrmDoseCov,by="dose")  
mmrmDoseRes$N1 <- trunc((mmrmDoseRes$SD/mmrmDoseRes$StdErr)^2,0)  
mmrmDoseRes$Glob_SD <- mmrm_global_sd  
mmrmDoseRes$N <- trunc((mmrmDoseRes$Glob_SD/mmrmDoseRes$StdErr)^2,0)  
...  
emaxMMRM_Int <-  
fitEmaxB(mmmrmDoseRes$Estimate,mmrmDoseRes$dose,prior_mmmrm,modType=4,count=mmrmDoseRes$N,  
msSat=mmrm_global_sd^2,mcmc=mc_mmmrm)
```

Model parameters, posterior medians and 90/95% credible intervals as specified in Section 5.2.6 will be output and provided back to the programming team after QC is complete.

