## Appendix 4. Traditional Statistical Methodology Details

The following SAS code is to be used as a guide for implementation.

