### Example SAS code for MMRM Model (strata included):

```
proc mixed data = dataset method=reml;
  class subject treatment time strata;
  model cfb = treatment base time base* time time *treatment strata/ddfm=kr residual outp=resid_out;
  repeated time /subject=subjid type = un;
  lsmeans treatment*time/diff cl alpha=0.1;
  ods output lsmeans=lsmeans_out;
  ods output diffs=diffs_out;
  ods output CovParms=CovParms_out;
run;
```

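### Does SAP 5.2.6 have to fix the strata weights for the by-arm LSMeans that feed the baseline-interaction Emax model?

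*SAP*

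**What the plan says.** SAP 6.1.1.2 lists two Emax fits among the supplementary analyses of the primary endpoint ("The following supplementary analyses to the primary endpoint will be carried out"). The fit in 5.2.5 uses the arm LSMeans from the pooled primary MMRM. The fit in 5.2.6 uses LSMeans from one MMRM per arm. For the by-arm models the SAP says "The MMRM models will include time and strata as fixed effects, baseline as a covariate", with a baseline-by-time term and no strata-by-time term. The reference point is given as "The LSmean results from the separate MMRM models will be calculated for the overall baseline HbA1c", meaning the baseline across all of Estimand Set 1A. No strata weights appear in the visible text. The strata wording in 5.2.3 is partly redacted.

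Appendix 3 tells the statistician to "take the average of the residual standard deviations from the separate MMRM outputs which will be used as the global standard deviation" and then computes "mmrmDoseRes$N <- trunc((mmrmDoseRes$Glob_SD/mmrmDoseRes$StdErr)^2,0" for each arm. A larger LSMean SE therefore becomes a smaller effective N in the Emax fit.

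The only MMRM code is in Appendix 4, introduced with "The following SAS code is to be used as a guide for implementation". It declares "class subject treatment time strata" and requests LSMeans for treatment by time with no weighting option.

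Protocol 4.1 limits diet-only participants to about 20% of those enrolled.

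**The concern.** Separate fits can be compared only at a common reference point. The SAP supplies one for baseline HbA1c but not for strata, the only other covariate besides time. If the by-arm code copies the LSMeans request in Appendix 4, and if the software weights the levels of a class factor equally by default (an assumption; the documents do not say so), three things follow.

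- Each arm mean, and E0, refers to a 50:50 population that the protocol does not allow to be enrolled.
- The by-arm SE is larger than it would be at the enrolled mix, so N falls and the Emax intervals widen.
- Each arm has its own strata coefficient, so the strata term does not cancel from the dose-placebo differences as it does in the pooled model. At a 20% share, a difference shifts by (0.5 - 0.2) = 0.3 times any dose-placebo difference in strata effect.

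The trial is meant to support dose selection, so an avoidable loss in a dose-response fit deserves a check.

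**Working it through.** **The plan's own figure.** Protocol 9.2 gives 50 completers per arm, SD 1.0, a difference of 0.5 and a 1-sided 5% test. The SE of the difference is 1.0 × √(2/50) = 0.20, and 0.5/0.20 = 2.5. Normal power is Φ(2.5 - 1.645) = 0.804, and the noncentral t with 98 df gives 0.799. The stated 80% is reproduced. The plan states no figure for the precision of the by-arm LSMeans.

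**By-arm SE under equal weights.** Let p be the diet-only share and S the six-visit covariance matrix. The strata effect is constant over time, so all six visits contribute to estimating it. The SE ratio, equal weights against enrolled mix, satisfies

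ratio² = 1 + [(0.5 - p)² / (p(1 - p))] × v, where v = [1/(1′S⁻¹1)] / S₁₆,₁₆.

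This agrees within 0.001 with a full GLS fit of the 5.2.6 model. At p = 0.2 the multiplier is 0.09/0.16 = 0.5625. At the enrolled mix, SE = 1/√50 = 0.141 and N = 50.

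Two cases by hand, with flat SD and compound symmetry:
- Correlation 0.5: v = (1 + 5 × 0.5)/6 = 0.583; ratio² = 1 + 0.5625 × 0.583 = 1.328; ratio 1.15; N = trunc(50/1.328) = 37.
- Correlation 0.85: v = (1 + 5 × 0.85)/6 = 0.875; ratio² = 1.492; ratio 1.22; N = 33.

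The documents give no visit covariances. Three SD patterns were therefore crossed with six correlation structures: compound symmetry 0.5, 0.7 and 0.85, and autoregressive 0.7, 0.85 and 0.9 per 4 weeks.

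| SD over Weeks 2-16 | v | SE ratio, 20% share | N | SE ratio, 10% share | N |
|---|---|---|---|---|---|
| 0.35 rising to 1.0 | 0.05-0.12 | 1.01-1.03 | 48-46 | 1.05-1.10 | 45-41 |
| 0.6 rising to 1.0 | 0.25-0.36 | 1.07-1.10 | 43-41 | 1.20-1.28 | 34-30 |
| flat at 1.0 | 0.58-0.88 | 1.15-1.22 | 37-33 | 1.43-1.60 | 24-19 |

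A flat SD is the less natural pattern, because the 120 mg arm reaches its target dose only in the seventh week (Protocol 4.2).

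**Effect on the Emax fit.** The inputs were the example means in Appendix 3, equal N in every arm, residual SD 1.0 and the SAP's t(5) priors with correlation -0.43. Vague normal priors (SD 10) were assumed for the redacted E0 and 120 mg difference. P50 is also redacted; 10 mg and 40 mg gave half-widths within 0.002 of each other. The 90% credible half-width for 120 mg minus placebo (% HbA1c) is:

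| N | 50 | 48 | 46 | 43 | 41 | 37 | 33 |
|---|---|---|---|---|---|---|---|
| Half-width | 0.274 | 0.280 | 0.285 | 0.295 | 0.302 | 0.316 | 0.333 |

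At a 20% share with rising SD, the interval is 2% (0.280/0.274) to 10% (0.302/0.274) wider. With flat SD it is 15-22% wider (0.316/0.274 to 0.333/0.274).

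**The pooled model and 5.2.5.** In the pooled MMRM the strata effect is common to all six arms, so it cancels from the dose-placebo contrasts, whose SE stays at 0.20 under either weighting. Section 5.2.5, however, takes arm LSMeans and arm SEs, not differences. The strata effect is estimated from six times the data, so the extra term is divided by 6: ratio² = 1 + 0.5625 × v/6. This gives 1.002-1.006 (N 49), 1.011-1.017 (N 48) and 1.027-1.040 (N 47-46) for the three SD patterns. On the same premise the 5.2.5 arm means and E0 would also refer to a 50:50 mix.

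**Whether the by-arm code can follow Appendix 4.** The Appendix 4 request is for treatment-by-time means, but a model fitted within one arm has no treatment term. It must also evaluate at the overall baseline, which the Appendix 4 line does not do. New LSMeans code has to be written in either case, and its strata weighting is not known.

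**The case for a change.** The case for acting is that the omission is real and cheap to close. The SAP standardises the by-arm means to a common baseline, and the same logic applies to strata. Neither obvious default gives a common enrolled mix: plain LSMeans would weight 50:50, and observed margins taken within each arm would use each arm's own mix. While the diet-only share is below one half, equal weights cannot be more precise than the enrolled mix. The 20% share is a ceiling, so the 20% columns show the mild end; at 10% the SE rises by 5-28% with rising SD and by 43-60% with flat SD.

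The direction and the arithmetic stand. The following weigh against a change.

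- The loss needs both an assumed default and a by-arm program copied from code that cannot be copied as it is.
- Equal-weight LSMeans are a legitimate convention. Changing 5.2.6 alone would, on the same premise, leave 5.2.5 at 50:50. The two Emax fits would then report E0 for different populations, and their comparison would mix the baseline interaction with the strata weighting.
- The analysis supports the primary one and does not replace it. Its fallback sets Hill to 1, then tries other priors, and only after that "otherwise an Emax model (with a baseline interaction) will not be reported".

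**Conclusion.** No change to the plan follows. The visible SAP leaves the strata weights unstated for the by-arm LSMeans, and the statistician who writes the by-arm code will have to choose them. That is a gap in detail, not an error in the analysis. Even under equal weights, the supplementary intervals remain valid if the strata effect does not differ by dose. At a 20% diet-only share they widen by about 2-10% when the SD rises over visits, which is 0.006-0.028% HbA1c on the half-width against a design difference of 0.5%. The 15-22% figure needs a flat SD from Week 2. The effect on 5.2.5 is an SE increase of about 0.2-4%. The primary estimates, their SEs and the power are untouched.

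The sizes rest on assumptions the documents do not settle: equal weighting by default, the visit covariances, the actual diet-only share and the redacted priors. A share well below 20% would make the loss in this one fit larger, as the 10% columns show. If the strata effect differed between a dose and placebo, the 5.2.6 difference would also move by 0.3 times that amount at a 20% share. Neither case would alter the primary conclusions.

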### 5.2.7. Cumulative Incidence Plots

Cumulative Incidence Plots will be produced based on the time to the event of interest (starting from the time of start of dosing on Day 1) for each treatment separately and will be plotted on the same graph up to Week 18 (i.e. including the follow-up visit 10). This will be based on plotting the cumulative incidence function (with no competing risks), which will be presented as a % on the y-axis. No statistical testing for differences between treatment will be considered.

Details of censoring are included in Section 6 and example SAS code is provided in Appendix 4.

### 5.3. Methods to Manage Missing Data

Details of efficacy data to be censored is described in Sections 3.2 and 3.3.

For applicable continuous endpoints modelled with an MMRM, missing/censored values will be imputed as part of the analysis method.

In all PK data presentations (except listings), concentrations below the limit of quantification (BLQ) will be set to zero. In listings BLQ values will be reported as “<LLQ”, where LLQ will be replaced with the value for the lower limit of quantification (LLQ).

#### 5.3.1. Multiple Imputation

For summarizing the proportion of responses in HbA1c CCI [REDACTED], all data from Estimand Set 2 CCI [REDACTED] will be included (i.e. all time points up to and including Week 16). A multiple imputation (MI) method will be implemented, using a multivariate imputation method by chained equations, which is still valid with an arbitrary missing data pattern. The model will include: treatment, baseline (HbA1c CCI [REDACTED]) and strata. Twenty sets of imputations of each missing value will be constructed from the MI method and the proportion of responses by treatment will be determined with associated standard errors utilizing a normal approximation and will be combined using standard multiple imputation techniques proposed by Rubin (2) to yield overall estimates. If there is more missing data in the study than anticipated, the number of imputation sets may be increased as required.

[REDACTED]

For logistic regression of HbA1c [CCI], all data from Estimand Set 2 [CCI] will be included (i.e. all time points up to and including Week 16). The same imputed datasets as produced for the proportion of responses above will be utilized, where a Logistic Regression model (as described in Section 5.2.4) will be applied to each of the 20 imputed datasets separately. Parameter estimates of the log odds ratios for each dose relative to placebo will be combined using standard multiple imputation techniques proposed by Rubin (2) to yield overall estimates of the log odds ratios and their associated standard errors will be used to create 90% confidence intervals on the log-odds scale. The log odds ratios and log odds 90% confidence intervals will be back transformed into odds ratios and associated 90% confidence intervals for final reporting.

## 6. ANALYSES AND SUMMARIES

Data collected before baseline will only be listed, unless otherwise stated.

### 6.1. Primary Endpoint(s)

#### 6.1.1. Change from Baseline in HbA1c at Week 16

##### 6.1.1.1. Main Analysis

In all cases the Estimand Set 1A as specified in Section 4 will be utilised.

Absolute values and changes from baseline in HbA1c will be summarised descriptively by treatment and time point as described in Section 5.2.1. Tables will present all data from the screening (visit 1, absolute tables only), beginning of the placebo run-in (visit 2, absolute tables only), baseline and post-baseline time points (including follow-up, which will be restricted to participants who completed 16 weeks of treatment and did not initiate glycaemic rescue medication). Box and whisker plots of absolute values and changes from baseline will also be separately produced.

The primary analysis will be an MMRM (as described in Section 5.2.3) applied to the change from baseline at Weeks 2, 4, 6, 8, 12 and 16 that will be used to estimate the treatment effect related to the primary Estimand 1A (as described in Section 2.1.1).

The following results from the above primary analysis will be plotted:

- Profile plots of the LSMeans (including 90% confidence intervals) over time, with a separate line for each treatment
- Profile plots of the LSMean differences to Placebo (including 90% confidence intervals) over time, with a separate line for each dose of PF-06882961
- Plot of the LSMeans (including 90% confidence intervals) at Week 16, with a separate point for each treatment (applicable to analyses related to HbA1c only)

- Plot of the LSMeans differences to Placebo (including 90% confidence intervals) at Week 16, with a separate point for each dose of PF-06882961 (applicable to analyses related to HbA1c only)

Standard SAS output will be provided to support the main statistical summary table for the primary analysis model but will not be included in the CSR.

In addition, a waterfall plot of the individual changes from baseline in HbA1c at Week 16 in the Estimand Set 1A will be created, ordered in increasing reductions from baseline and coloured by treatment.

